8.3.4. Pregnancy

Sexually active WOCBP must use an effective method of birth control during the course of the study, in a manner such that risk of failure is minimized. Before enrolling WOCBP in this clinical study, the investigator must review the guideline about study participation for WOCBP which can be found in the GCP Manual for Investigators. The topics include the following:

- General Information
- Informed Consent Form
- Pregnancy Prevention Information Sheet
- Drug Interactions with Hormonal Contraceptives
- Contraceptives in Current Use
- Guidelines for the Follow-up of a Reported Pregnancy.

Before study enrollment, WOCBP must be advised of the importance of avoiding pregnancy during study participation and the potential risk factors for an unintentional pregnancy. The subject must sign an informed consent form documenting this discussion.

All WOCBP MUST have a negative pregnancy test within 72 hours before receiving ipilimumab. The minimum sensitivity of the pregnancy test must be 25 IU/L or equivalent units of HCG. If the pregnancy test is positive, the subject must not receive ipilimumab and must not be enrolled in the study.

In addition, all WOCBP should be instructed to contact the investigator immediately if they suspect they might be pregnant (e.g., missed or late menstrual period) at any time during study participation.

If, following initiation of the investigational product, it is subsequently discovered that a study subject is pregnant or may have been pregnant at the time of investigational product exposure, including during at least 6 half-lives after product administration, the investigational product will be permanently discontinued in an appropriate manner (eg, dose tapering if necessary for subject safety). The investigator must immediately notify the Sponsor of this event and record the pregnancy on the Pregnancy Surveillance Form (not an SAE form). Initial information on a pregnancy must be reported immediately to the Sponsor, and the outcome information provided once the outcome is known. Completed Pregnancy Surveillance Forms must be forwarded to the Sponsor according to SAE reporting procedures.

Any pregnancy that occurs in a female partner of a male study participant should be reported to the sponsor. Information on this pregnancy will be collected on the Pregnancy Surveillance Form.

Protocol-required procedures for study discontinuation and follow-up must be performed on the subject unless contraindicated by pregnancy (e.g., x-ray studies). Other appropriate pregnancy follow-up procedures should be considered if indicated. In addition, the investigator must report to the Sponsor, and follow-up on information regarding the course of the pregnancy, including perinatal and neonatal outcome. Infants should be followed for a minimum of 8 weeks.

8.3.5. Other Safety Considerations

Any significant worsening noted during interim or final physical examinations, electrocardiograms, x-rays, and any other potential safety assessments, whether or not these procedures are required by the protocol, should also be recorded in the medical record.

9. STATISTICAL METHODOLOGY

9.1. Sample size.

The primary endpoint in this study is the 1-year actual survival rate. A one-stage Fleming design has been adopted. Assuming a historical 1-year survival rate of 20% (with radiation therapy + best supportive care) for the selected population, a sample size of 56 evaluable patients would be needed to show that the addition of ipilimumab to radiotherapy generates a 1-year survival rate of 35%, reaching 80% power at the 0.05 significance level.

A total of 56 evaluable patients would need to be included. In case that at least 17 out of these 56 evaluable patients would survive for at least one year, the conclusion of the trial would be that the higher 1-year survival rate of 35% is more likely for the combination than the historical 20% survival rate.

9.2 Populations for Analyses

- Enrolled Subjects: All subjects who signed and informed consent form and were registered.
- Treated Subjects (Safety Population): Includes all subjects in the study who receive at least one dose of ipilimumab. Unless otherwise indicated, analyses of drug exposure and safety will be performed on this population as treated.

- Evaluable Subjects: Includes all subjects who received at least 1 dose of ipilimumab and the full WBRT therapy.
- Biomarker Subjects: Includes all treated subjects with at least baseline biomarker studies.

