Study Schema: Drugs / Doses / Length of Treatment)	
 • Ipilimumab 3mg/Kg iv q 3 weeks for 4 cycles • WBRT 30 Gy in 10 fractions (or radiobiological equivalent schedule, after Sponsor approval), starting between C1D2 and C2D1
Study Objectives: Primary: Secondary:	
Primary Objective
 
 • Efficacy - Primary endpoint: 1-year survival rate 
Secondary Objectives
 
 • Efficacy – Endpoints: 
 ○ Progression-Free survival-PFS (median, 6-month PFS rate) 
 ▪ Intracranial PFS (median, 6-month PFS rate)

	
 ▪ Extracranial PFS (median, 6-month PFS rate) 
 ○ Overall survival (median) ○ Response rate: (global, intracranial, extracranial) (“Immune-related response criteria”) ● Safety: Adverse Event rates ● Feasibility: dose delays/reductions, treatment exposure
Study Design:	Multicenter, single arm, phase 2 clinical study on the combination of radiation therapy and ipilimumab
Accrual Goal: (Total number of patients)	56 patients treated 66 included
Accrual Rate: (Number of patients expected per month)	3 to 4 patients per month
FPFV: LPFV: Follow Up: (dd-mm-yy)	03/2014 10/2015 10/2016
Correlative Studies: (PK/PD, etc.)	
Exploratory Objectives.
 
 ○ Potential baseline predictors of efficacy (in tumor tissue and peripheral blood) 
Potential early surrogates for response: inpatient variation of quantitative apparent diffusion coefficients of serial diffusion-weighted magnetic resonance imaging

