2.2 Secondary Objectives

- Efficacy – Endpoints:
 - Progression-Free survival-PFS (median, 6-month PFS rate)
 - Intracranial PFS (median, 6-month PFS rate)
 - Extracranial PFS (median, 6-month PFS rate)
 - Overall survival (median)
 - Response rate: (global, intracranial, extracranial) (“Immune-related response criteria”)
- Safety: Adverse Event rates
- Feasibility: dose delays/reductions, treatment exposure

2.3. Exploratory Objectives.

- Potential baseline predictors of efficacy (in tumour tissue and peripheral blood – see 6.4.3.)
- Potential early surrogates for response: inpatient variation of quantitative apparent diffusion coefficients of serial diffusion-weighted magnetic resonance imaging

⁶⁸ Hodi FS, O'Day SJ, McDermott DF, et al. Improved survival with ipilimumab in patients with metastatic melanoma. *N Engl J Med.* 2010 Aug 19;363(8):711-23.

⁶⁹ http://www.ema.europa.eu/docs/en_GB/document_library/EPAR_-_Product_Information/human/002213/WC500109299.pdf

3 **STUDY DESIGN**

This is a non-controlled, single stage, multicenter phase 2 clinical study. A total of 56 evaluable patients will be treated in this study.

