- Main eligibility criteria are: patients with melanoma and brain metastases, adequately fit (ECOG PS 0 to 1; Barthel Index > 10/20) and of intermediate prognosis according to the RPA classification (Table 1). These patients must not have cerebral metastases for which local therapy (neurosurgery, radiosurgery) might achieve a disease-free status; they must not be experiencing a rapid clinical deterioration, risk of herniation; patients must not require unstable ascending dosing of supportive medication in the last week -including anti-convulsivants, steroids and analgesics-, or dexamethasone > 16 mg/day (or other glucocorticoid at an equivalent dose); patients must not have a high LDH (> 2 x ULN), they must not have an uncontrolled diabetes mellitus (HbA1c > 9%) and must be suitable for receiving an anti CTLA4 (i.e. not having any autoimmune-mediated co-morbidities). Patients must have not received prior therapy for brain metastases. Screening stage: Once the ICF is signed by the patient and investigator, patients will be sequentially registered at the Spanish Melanoma Group Datacenter or delegated CRO, by submitting a “registration form”. A Patient Identification Number will be provided by the Sponsor. A second form, the “eligibility checklist”, will be sent by the investigational site once the screening phase has been completed, either if the patient becomes eligible or if he/she results in a screening failure. No protocol exceptions will be permitted by the sponsor.

Patient inclusion:

[figure not shown]
After confirming that a patient is a candidate for inclusion in this study (inclusion / exclusion), the subject will be assigned a code of patient centralized (registration or inclusion of patients).

The process of enrolling patients described below:

1. Complete and sign the inclusion of the patient (the registration form must be signed by a clinical Principal Investigator or designated appropriately identified in the list of signatures and recording studio delegation of responsibilities).
2. Send the completed and signed form to:

██
██

3. ██████████ will register the patient and
 4. will send the inclusion confirmation form to the site, both by fax and email. Confirmation of patient inclusion will contain the patient number, which identifies subjects in the trial.
 5. Once the site has received the confirmation of inclusion for the patient, the patient can begin receiving protocol treatment.

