9.3 Endpoint Definitions

9.3.1 Primary Endpoint

Actuar survival rate at 1 year since the first dose. Overall survival status will be ascertained, at a minimum, every 12 weeks from first ipilimumab dose.

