9.3.1.1 Overall Survival (OS)

OS is defined for each subject as the time between the date of the first dose of ipilimumab and death. If a subject has not died, the subject will be censored at the time of last contact (last known alive date).

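### The primary 1-year survival test drops treated patients who die before finishing whole-brain radiotherapy, although survival is counted from the first ipilimumab dose

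*Protocol*

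**What the plan says.** Protocol 9.1 sets a one-stage Fleming design: 20% against 35% 1-year survival, 80% power, 0.05 level. It states that "A total of 56 evaluable patients would need to be included" and ties success to one count: "In case that at least 17 out of these 56 evaluable patients would survive for at least one year". Section 9.2 defines that population: "Evaluable Subjects: Includes all subjects who received at least 1 dose of ipilimumab and the full WBRT therapy".

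The clock starts earlier than that definition can be met. Section 9.3.1 gives the primary endpoint as "survival rate at 1 year since the first dose", and 9.3.1.1 says that "OS is defined for each subject as the time between the date of the first dose of ipilimumab and death". Section 9.4.2.1 also counts the year from the first ipilimumab administration. Under section 3 (Treatment Phase), WBRT begins between the first and second ipilimumab doses, which are three weeks apart. Section 5.2 gives it in 10 daily fractions.

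SAP 1.5 and 1.5.1 carry the evaluable set into the efficacy and survival tables. SAP Table 14 records premature end of radiotherapy, with a reason. SAP 1.9 lists deaths among treated patients. In the text available, no section tests 1-year survival in all treated patients; SAP 1.1, which the SAP cites for the evaluable count, is not available.

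The numbers to be recruited are not stated consistently. The synopsis accrual goal reads "56 patients treated 66 included", while section 3 says "A total of 56 evaluable patients will be treated in this study".

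**The concern.** Membership of the primary set depends on something that happens after time zero. With WBRT starting within three weeks of the first dose and lasting about two weeks (assuming five fractions a week), it is settled about 2 to 5 weeks into follow-up. Every evaluable patient has, by definition, lived long enough to finish WBRT. This is immortal-time selection.

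Two things are at stake. The estimated 1-year survival is biased upward when the excluded patients survive less often than treated patients as a whole, as is certain for those who die during WBRT. And the trial's only decision rule may not hold its 5% level, because a 20% benchmark for everyone who starts treatment would be compared with a proportion among selected patients. The margin is thin: the exact alpha is 0.043 before any selection.

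The visible text does not say whether non-evaluable patients are replaced, or what cut-off applies with fewer than 56 evaluable. The size of the error therefore depends on choices the plan leaves open.

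**Working it through.** **Inputs.** p0 = 0.20, p1 = 0.35, n = 56 and cut-off 17, all from protocol 9.1. The fraction of treated patients excluded for not completing WBRT, e, and their 1-year survival, s, are not in the documents; both are assumptions and are varied. All tails are exact binomial and one-sided. The protocol does not state sidedness, but the rule reproduces as one-sided.

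**The plan's own figure.** P(X ≥ 17 | 56, 0.20) = 0.0432 and P(X ≥ 17 | 56, 0.35) = 0.8064. The design is correct for 56 unselected patients.

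**Case A: 56 completers are accrued, so more than 56 are treated.** If 1-year survival is 20% in everyone treated, survival among completers is p = (0.20 − e·s)/(1 − e), and alpha = P(X ≥ 17 | 56, p). With s = 0:

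| Excluded / treated | e | p among completers | Alpha |
|---|---|---|---|
| 0 / 56 | 0 | 0.2000 | 0.0432 |
| 1 / 57 | 1.75% | 0.2036 | 0.0501 |
| 2 / 58 | 3.45% | 0.2071 | 0.0577 |
| 3 / 59 | 5.08% | 0.2107 | 0.0661 |
| 4 / 60 | 6.67% | 0.2143 | 0.0753 |
| – | 10% | 0.2222 | 0.0990 |

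Alpha reaches 0.05 at e = 1.74%. A true 35% would on average be reported as 0.35/0.95 = 36.8% at e = 5%, and as 0.35/0.90 = 38.9% at e = 10%.

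Allowing some excluded patients to survive the year:

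| e | s = 0 | s = 0.10 | s = 0.20 | s = 0.30 |
|---|---|---|---|---|
| 5% | 0.066 | 0.054 | 0.043 | 0.034 |
| 10% | 0.099 | 0.067 | 0.043 | 0.026 |

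As an illustration only, a constant hazard giving 20% survival at one year has 6.0%, 8.8% and 14.3% dead by weeks 2, 3 and 5. Using these as e with s = 0 gives alpha of 0.071, 0.090 and 0.140.

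**Case B: exactly 56 are treated and 17 evaluable survivors are still required.** Alpha = P(X ≥ 17 | 56, 0.20 − e·s) and power = P(X ≥ 17 | 56, 0.35 − e·s). Alpha never exceeds 0.0432. At e = 5%, power is 0.806, 0.784, 0.761 and 0.723 for s = 0, 0.10, 0.20 and 0.35.

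**Case C: 56 treated, m evaluable, cut-off re-derived for m.** The plan does not propose this, but does not rule it out. If the excluded all die, survival among completers is 56 × 0.20/m = 11.2/m. For m = 53 to 55 the cut-off stays at 17 and alpha is 0.042 to 0.043. For m = 49 to 52 it falls to 16 and alpha is 0.076 to 0.077.

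**The case against.** The inflation needs three conditions that the documents do not establish: that non-completers are replaced, that the 20% describes everyone who starts treatment, and that nearly all the excluded die within the year.

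- **Replacement.** The synopsis fixes 56 treated. The 10 extra included patients may be people who were never dosed, since section 3 requires the eligibility form "either if the patient becomes eligible or if he/she results in a screening failure". On that reading Case B applies and alpha is controlled.
- **Benchmark.** Section 9.1 describes it only as radiotherapy plus best supportive care in the selected population. If it came from completers, alpha stays at 0.043.
- **Survival of the excluded.** Early stopping of radiotherapy is not always death. At s = 0.20 the inflation is gone, and above that the bias reverses.

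Eligibility also keeps early deaths down: section 4 excludes rapid deterioration, herniation risk and LDH above twice the upper limit, and requires Karnofsky above 70. And early deaths would be visible in SAP Table 57, which lists survival time from the first cycle.

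All of this limits the size, and the inflation must be stated as conditional. It does not remove the defect. Sections 9.1 and 3 both fix 56 evaluable, which supports accruing beyond 56 treated. Eligibility makes early death less likely but does not rule it out, and one excluded death in 57 uses up the whole margin. A listing of deaths is not a test. In Case B alpha holds, but dividing by the evaluable number still overstates survival when deaths are excluded.

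**Conclusion.** The concern holds and should be fixed. That the primary set is selected on an event after time zero follows directly from 9.1, 9.2 and 9.3.1, and is carried into the SAP; this part is certain.

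The size is conditional. With 56 completers accrued, a benchmark that applies to all starters, and excluded patients who die within the year, alpha passes 5% at about 1 exclusion in 57 treated, though only just (0.0501). It is about 0.066 at 5% excluded and 0.099 at 10%, and a true 35% is reported as 36.8% and 38.9%. With only 56 treated and 17 still required, there is no inflation, and power falls below 0.806 if any of the excluded would have survived. Since the plan does not settle which of these applies, the stated 5% level cannot be taken as assured.

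**What to change.** Make all patients who receive at least one ipilimumab dose the primary population for 1-year survival, count deaths before WBRT completion as failures, and keep the full-WBRT set as a sensitivity analysis. Prespecify the cut-off by number treated, each with exact one-sided alpha at or below 0.05 against 20%:

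| Treated | Survivors required | Alpha | Power at 35% |
|---|---|---|---|
| 56 | 17 | 0.043 | 0.806 |
| 57 | 18 | 0.026 | 0.749 |
| 58 | 18 | 0.031 | 0.778 |
| 59–61 | 18 | 0.037–0.0496 | 0.804–0.850 |
| 62–65 | 19 | 0.031–0.049 | 0.802–0.866 |
| 66 | 20 | 0.031 | 0.823 |

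Reconcile 56 treated (synopsis) with 56 evaluable (9.1 and section 3), state whether non-evaluable patients are replaced, and state which patients the 20% describes. Amend 9.1, 9.2 and SAP 1.5 to match. As a separate correction, use treated patients as the denominator for response and disease control in SAP 1.5.3, as protocol 9.3.2.2 and 9.3.2.3 define them.

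The cost is wording: survival is already followed in treated patients. The estimate may be slightly less favourable, and treating more than 56 raises the cut-off. Because 57 or 58 treated gives less than 80% power, the target should be fixed at 56 or at 59 and above.

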9.3 Endpoint Definitions

9.3.1 Primary Endpoint

Actuar survival rate at 1 year since the first dose. Overall survival status will be ascertained, at a minimum, every 12 weeks from first ipilimumab dose.

9.3.1.1 Overall Survival (OS)

OS is defined for each subject as the time between the date of the first dose of ipilimumab and death. If a subject has not died, the subject will be censored at the time of last contact (last known alive date).

9.3.2 Secondary and Exploratory Endpoints

The secondary endpoints will be based upon tumor assessments which are performed as described in section 6.2. until progression by irRC, intolerable toxicity, or withdrawal of consent. Response based endpoints will be evaluated based on mWHO criteria for secondary endpoints and irRC for exploratory endpoints (see Section 6.2 for definitions).

9.3.2.1 Progression Free Survival (PFS)

PFS is defined for each subject as the time between the date of the first dose of ipilimumab and the date of progression or death, whichever occurs first. A subject who dies without reported prior progression will be considered to have progressed on the date of death. For a subject who undergoes tumor resection on study, PFS will be censored on the date of the last tumor assessment prior to resection. For those who remain alive and have not progressed, PFS will be censored on the date of last tumor assessment. For subjects who have PD prior to Week 12 and a subsequent assessment of SD, PR or CR, the date of PD following response (where available) will be used in the analysis of PFS; otherwise these subjects will be censored on the date of their last tumor assessment.

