- The trial schema is represented in the following figure:

All individual patient registered into the trial should undergo the screening phase of the study. Patients consenting, registered and eligible will subsequently proceed through the treatment and follow up phases of the trial.

- **Screening Phase**

- It initiates after the written informed consent is obtained and the patients is registered. In this phase the assessment of the subject's eligibility to participate will be done, as determined by the inclusion/exclusion criteria.

- **Treatment Phase**

- Treatment will consist in the administration of ipilimumab and WBRT. The dose of ipilimumab will be 3 mg/kg, administered intravenously over a 90-minute period every 3 weeks, for a total of four doses. Standard WBRT should be initiated between the first and second dose of ipilimumab. The dose of radiation therapy will be 30 Gy over 10 fractions. Radiobiologically equivalent doses might be acceptable, but require discussion and approval of the Sponsor.
- Laboratory evaluations should be performed and the results examined before administration of each ipilimumab dose, with the exception of hormone results. For these latter parameters it is required that at least the results of the tests performed within the last 3 weeks are available and normal.
- As durable disease stabilization and/or objective tumor response can be seen after early progression before Week 12, it is recommended that, in the absence of dose-limiting toxicities

(eg, serious immune-mediated adverse reactions), all four doses of ipilimumab be administered over the initial 12 weeks even in the setting of apparent clinical progression, providing the subject's performance status remains stable.

- All subjects who enter the treatment period, including those who may have discontinued treatment for drug-related AEs and/or who have evidence of clinical progression during the induction period, should obtain a 12-week tumor assessment.
- Based on clinical experience in the ongoing and completed melanoma studies, the following recommendations apply for subject management in light of the Week 12 or later tumor assessments:

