- Progressive Disease (PD): Appearance of any new lesion(s) and/or unequivocal progression of non-index lesion(s) (eg, an increase in pleural effusions, or other fluid collections defined as an approximate doubling of the volume which was present at baseline or nadir, unless there is radiographic evidence of a benign cause for the fluid collection or the effusion is cytologically negative for malignant cells).

6.4.2.f Response per Time Point

OR is determined as the combination of assessments of index and non-index lesions using the following criteria presented in Table 13

Table 13: Overall Response per mWHO

Index Lesions	Non-index Lesions	New Lesions	Overall Response
CR	CR	No	CR
CR	IR/SD	No	PR
PR	CR or IR/SD	No	PR
SD	CR or IR/SD	No	SD
PD	Any	Yes or No	PD
Any	PD	Yes or No	PD
Any	Any	Yes	PD

6.4.2.g Best Overall Response (BOR)per Subject (Including all TimePoints)

BOR is the best confirmed response designation over the study as a whole, recorded between the date of first dose until the last tumor assessment prior to subsequent therapy (except for local palliative radiotherapy for painful bone lesions) for the individual subject in the study. The assessment of response at 12 weeks has particular emphasis due to the mechanism of action of ipilimumab inducing immune responses as basis for clinical responses. For the assessment of BOR, all available assessments per subject are considered. CR or PR determinations included in the BOR assessment must be confirmed by a second (confirmatory) evaluation meeting the criteria for response and performed no less than 4 weeks after the criteria for response are first met.

Consistent with the definition of BOR in this study, the date of disease progression is defined for each subject based on post-Week 12 time points, in cases where a subject had an OR of CR, PR or SD at Week 12. BOR assessment of SD requires an OR of SD (or unconfirmed PR or CR) at Week 12, in the absence of BOR of CR, PR or PD.

The following criteria (Table 14) summarize the combination of assessments of OR at different time points throughout the study to establish BOR for the individual subject with emphasis on the 12 week time point due to the mechanism of action of ipilimumab:

Table 14. Assessment of Best Overall Response

Overall Response At Time Points Before Week 12	Overall Response At Week 12	Overall Response At Time Points After Week 12	Best Overall Response For All Time Points
CR* or PR*	Any	Any	CR or PR (at time point before Week 12)

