9.3.2.5 Duration of Stable Disease

Duration of stable disease is defined for subjects whose BOR is SD as the time between when SD is first documented and the date of PD or death (whichever occurs first). For a subject who undergoes tumor resection following Week 12 but prior to disease progression, duration of stable disease will be censored on the date of the last evaluable tumor assessment prior to resection. For subjects who have BOR of SD at Week 12, the date of PD following thereafter (where available) will be used in the analysis of duration of stable disease. For subjects with BOR of SD who have not subsequently progressed and who remain alive, duration of stable disease will be censored on the date of last evaluable tumor assessment.

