1.5.2. PROGRESSION-FREE SURVIVAL (Evaluables)

Following the protocol, the population of was used for the efficacy analysis evaluable patients: n = X (see section 1.1)

According to protocol: PFS is defined in each patient as the time between the date of the first dose of ipilimumab and the date on which progression is determined or death occurs, whichever occurs first. If a patient dies without prior notification of progression, progression will be considered to have occurred on the date of death. For a patient who undergoes tumor resection during the study, the PFS will be censored on the date of the last tumor evaluation prior to resection. In the case of patients who remain alive and do not show progression, the PFS will be censored on the date of the last tumor evaluation. For patients in whom PE has been determined before week 12 and a subsequent evaluation of EE, PR, or CR is obtained, the date of PE after response (if available) will be used in the analysis. of the SLP; otherwise, these patients will be censored on the date of their last tumor evaluation.

Table 29. Progression-free survival (evaluable)

Estimated progression-free survival	N events	N at risk	% of patients without progression	95% CI	with progression
at 6 months					
to 12 months					
	N (%)	Median	Min-Max	Standard Error	Confidence interval 95%
Estimated progression-free survival					

Table 30. Progression-free survival and PFS at 6 months (Evaluable)

		N (%; 95% CI)
Progression-free survival	Alive (without PE)	
	PE	
	Exitus (without prior PE)	
	Total	
PFS at 6 months (crude)	No	
	Yes	
	No follow-up at 6 months (or PE before 6m)	
	Total	
PFS at 6 months (crude) (excluding patients with follow-up <6 months and no PE / previous death)	No	
	Yes	
	Total	

Figure 3. Survival free of Estimated progression (Evaluable)

Table 31. Time to PE (only in patients with PE)

	N	Mean (SD)	Median (Min-Max)
Time to PFS (months from 1st cycle of Ipilimumab) (only patients with PE)			

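### The PFS rule lets a tumour assessment made after non-study therapy cancel a progression before Week 12, and its resection rule does not say that resection must come before progression

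*Protocol*

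**What the plan says.** **PFS, protocol 9.3.2.1.** PFS runs between "the date of the first dose of ipilimumab and the date of progression or death, whichever occurs first". Two special rules follow.

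- *Early progression.* "For subjects who have PD prior to Week 12 and a subsequent assessment of SD, PR or CR, the date of PD following response" is used where it exists; "otherwise these subjects will be censored on the date of their last tumor assessment". The rule does not mention subsequent therapy.
- *Resection.* "For a subject who undergoes tumor resection on study, PFS will be censored on the date of the last tumor assessment prior to resection". The rule does not say whether progression may already have occurred.

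**SAP 1.5.2** carries the definition over ("For patients in whom PE has been determined before week 12 and a subsequent evaluation of EE, PR, or CR is obtained") with no therapy cut-off.

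**Neighbouring definitions are tighter.**

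- BOR (protocol 6.4.2.g) counts assessments "recorded between the date of first dose until the last tumor assessment prior to subsequent therapy", with palliative radiotherapy to painful bone lesions excepted. irBOR (6.4.2.k) has the same limit.
- Duration of stable disease (9.3.2.5) censors for resection only when the patient "undergoes tumor resection following Week 12 but prior to disease progression". Duration of response (9.3.2.4) has no such condition.

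**Follow-up.** Under Study Design (protocol Section 3, Treatment Phase), all who start treatment, including those "who have evidence of clinical progression during the induction period, should obtain a 12-week tumor assessment". The follow-up part of that section says that patients who stop for clinical progression and switch treatment are formally followed only for death. Section 5.4.1 prohibits non-study anti-cancer agents during the study. Under 9.3.2, assessments end at irRC progression, intolerable toxicity or withdrawal of consent; starting another therapy is not listed.

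**The concern.** The early-progression rule has a sound purpose. Ipilimumab can produce late responses after apparent growth, and protocol 6.4.2.i says so. As worded, however, the later SD, PR or CR need not be attributable to study treatment. A patient who progresses early, switches to another drug and then has a scan showing control would lose the progression event. The same scan would be inadmissible for BOR.

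The resection wording raises a similar problem. A patient with progression on the Week 12 scan whose lesion is then removed could be coded as an event at Week 12 or as censored at Week 12, depending on which sentence the analyst follows.

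Median and 6-month PFS, overall, intracranial and extracranial, are named secondary endpoints. There is no control arm in which the same effect could offset the shift.

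**Working it through.** The plan gives no PFS target, so there is no planned PFS figure to reproduce. The check has three steps: whether the route is open, which way the error goes, and how large it could be.

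**1. Is the route open?** Three things must occur together.

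- *Progression before Week 12.* The first scheduled post-baseline scan is at Week 12 (6.4.2), so this needs an extra scan. Section 6.4.2.c allows one on suspicion of progression, and Table 14 has a column for time points before Week 12.
- *A switch to other therapy.* Section 5.4.1 prohibits it during the study, and Section 3 recommends all four doses despite apparent clinical progression if performance status is stable. Section 3 nevertheless provides for patients who have switched, and BOR's cut-off presupposes them.
- *A later SD, PR or CR on record.* Section 3 asks for the 12-week assessment even after clinical progression. With formal follow-up then reduced to death, a later progression may never be recorded, and the censoring clause applies.

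The route is narrow but not closed.

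**2. Direction.** Replacing an event with a later event or a later censoring time cannot lower the Kaplan-Meier curve.

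**3. Size, under stated assumptions.** Inputs:

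- n = 56 evaluable patients (protocol 9.1).
- Exponential PFS with median 2.8 months. This is borrowed from the ipilimumab arm of CA184024 (protocol 1.3.5.c), not from this population.
- k affected patients. The documents give no value for k.

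Baseline values, with Week 12 = 84/30.44 = 2.76 months:

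- S(6) = 0.5^(6/2.8) = 0.226
- S(2.76) = 0.5^(2.76/2.8) = 0.505
- Conditional survival from Week 12 to month 6 = 0.226/0.505 = 0.448

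*Case A, early progression cancelled and patient censored at Week 12.* The curve at Week 12 rises by k/56, and 0.448 of that rise carries to month 6: S(6) = 0.226 + 0.448 × k/56.

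*Case B, early progression cancelled and the next progression after month 6.* S(6) = 0.226 + k/56.

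| k | Case A | Case B |
|---|---|---|
| 0 | 22.6% | 22.6% |
| 1 | 23.4% (+0.8) | 24.4% (+1.8) |
| 3 | 25.0% (+2.4) | 28.0% (+5.4) |

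Simulation of 4,000 trials under the same model agrees: about 22.5% at k = 0 and, for k = 3, about 25% (A) and 28% (B). The typical estimated median for k = 3 in Case A rises from 2.7 to 3.2 months.

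For scale, the standard error of a 22.5% rate with 56 patients is √(0.225 × 0.775/56) = 0.056, or 5.6 points.

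**Resection.** No rate of resection after progression is given, so no size is claimed. The texts compare as follows.

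| Section | Must resection precede progression? |
|---|---|
| 9.3.2.1 PFS | Not stated |
| 9.3.2.4 Duration of response | Not stated |
| 9.3.2.5 Duration of stable disease | Yes |

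For PFS, the base definition (first of progression or death) makes an earlier progression the event; the unconditional resection sentence censors the same patient. The two conflict only when resection follows progression.

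**The case against.** The strongest reply is that the rule is deliberate and the problem rare. Cancelling an early progression after later disease control matches the emphasis on Week 12 in Table 14 and the rationale in 6.4.2.i. An affected patient needs an unscheduled scan, an early switch that the protocol discourages, and a scan after the switch, when formal follow-up has been reduced to death. Whether the 12-week scan is expected in patients who have already switched is itself unclear. With no such patient there is no bias. PFS has no hypothesis, alpha or target, and three affected patients in Case A shift the estimate by less than half a standard error. All of this stands. It limits the likely size but does not tell the analyst what to do when the case arises.

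Several stronger readings are tempting and are not supported:

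- *That PFS is biased upward as a fact.* The documents support only that it can be, and only in that direction.
- *That the plan censors resected patients after progression.* The base definition in the same section points the other way, so this is a conflict in wording.
- *That an affected patient is event-free at 6 months and a failure for BOR.* In Case A the patient is censored at about 2.8 months, and the SAP's crude table has a separate row for no follow-up at 6 months. Table 14 has no row for early progression without usable Week 12 data.
- *That the 39% dabrafenib response rate in protocol 1.2.4 measures the likely salvage effect.* That figure is for untreated V600E brain lesions. Radiotherapy here starts by cycle 2, so the 31% reported after prior local treatment is closer.

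**Conclusion.** The point holds in conditional form. As written, 9.3.2.1 and SAP 1.5.2 allow a response to non-study therapy to remove an early PFS event, which the protocol's own BOR and irBOR definitions do not allow. Any resulting error in median or 6-month PFS is upward. On the assumptions used (n = 56, exponential PFS, 2.8-month median), it is about 1 to 2 points on 6-month PFS for one affected patient and about 2.5 to 5.5 for three. The documents do not say how many there would be; the conditions suggest few.

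The resection wording is a separate, smaller defect: two sentences in 9.3.2.1 give different answers for a patient resected after progression, and 9.3.2.4 lacks the same condition.

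The trial's conclusion rests on 1-year survival, which neither rule touches. The reason to act is that the change is cheap and brings PFS into line with definitions the protocol already uses.

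**What to change.** 1. In protocol 9.3.2.1 and SAP 1.5.2, apply the early-progression override only when the later SD, PR or CR assessment precedes any subsequent non-study anti-cancer therapy, with palliative bone radiotherapy excepted as in 6.4.2.g. Otherwise the first progression date is the event.
2. In protocol 9.3.2.1 and 9.3.2.4 and the matching SAP text (1.5.2 and the duration-of-response paragraph in 1.5.3), limit the resection rule to resection that occurs before progression, as 9.3.2.5 does.
3. Apply both rules to intracranial and extracranial PFS.

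The cost is a few sentences in each document and the start date of the first subsequent anti-cancer therapy for each patient. Reported PFS may be slightly lower.
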